6.2. KEY DEFINITIONS

6.2.1. Baseline

Unless otherwise specified, baseline will be defined for each subject and will be defined as the last available, valid, non-missing assessment reported on or before the start of first study drug administration.

6.2.2. Study Day

The date of first dose of study drug is designated as Day 1. Study days for screening visits are negative numbers and there will be no study day 0.

Study day will be calculated relative to first study drug administration. If the date of interest occurs on or after the first study drug administration date, study day will be

Amendment Final V 2.0

calculated as (date of interest - first study drug administration date) + 1. If the date of interest occurs prior to the first study drug administration date, study day will be calculated as (date of interest - first study drug administration date).

A subject's treatment end date is defined by the subject's last dose date in the study. A subject's study end date is defined by the date of the subject's last assessment in the study.

6.2.3. Change from Baseline /Percent Change

CFB (Change from baseline) = Post-baseline assessment - baseline assessment

PCFB (Percent Change from baseline) = (Post-baseline assessment - baseline assessment)/baseline assessment

6.3. MISSING DATA

Subjects who discontinue the study prematurely will not be replaced. No imputation will be made for missing data. All analyses will be based on available data, unless otherwise stated. Subjects Incomplete or missing data will be presented in the listings as they were reported on the CRFs.

Missing or incomplete dates for AEs and concomitant medications will be imputed as needed only to determine treatment emergence or distinguish between prior and concomitant medications.

If an AE has a missing onset date, then the AE will be considered a TEAE unless a non-missing stop date indicates otherwise. A medication with a completely missing start date will be considered a prior medication. A medication with a missing stop date will be considered a concomitant medication.

If an AE or a medication has a partial start or stop date, the following rules will be used to determine whether it is an AE or a TEAE, a prior or a concomitant medication.

Date imputation rules for medications and adverse events are summarized in Table 1.

Table 1 Imputation of Missing Dates

Partial Missing Start or Stop Date	Imputed Start Date	Imputed Stop Date
Missing month and day but the year is present	January 1 of that year or first dose date if the year is the same as the first dose date	December 31 of that year
Missing day but the year and month are present	First day of that month or first dose date if the year and month are the same as the year and month of first dose date.	Last day of that month

Amendment Final V 2.0

Note: If the imputed start date is after the stop date, then the start date will be set to equal the stop date.

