#### **12.10.8 Concomitant Medications**

Concomitant medications will be classified using the current version of the World Health Organization Drug Dictionary Enhanced (2012). Concomitant medications are medications taken at least once from 28 days prior to Screening through the End of Study visit.

Medications stopped on the 28 days prior to Screening time point will not be considered a concomitant medication.

Individual data listings will be presented for each subject, with separate listings for prior medications and concomitant medications. In addition, concomitant medications will be summarized by Anatomical Therapeutic Chemical (ATC) classes and PT using frequency counts and percentages. For the summaries of concomitant medications, subjects who take the same medication (in terms of the preferred term) more than once will be counted only once for that medication.

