7.4.1. Prior Medication

Prior medications are medications that were stopped ≥ 28 days prior to screening visit.

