7.4.2. Concomitant Medication

Concomitant medications are any medications started between 28 days prior to Screening through the End of Study visit.

Amendment Final V 2.0

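### SAP 6.3 calls a medication with a completely missing start date prior whatever its stop date: a drug stopped on study is misfiled, and a drug with both dates missing gets two classes

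*SAP*

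**What the plan says.** SAP 6.3 (Missing Data) states that medication dates are "imputed as needed only to determine treatment emergence or distinguish between prior and concomitant medications". Two consecutive sentences then deal with dates that are absent. The first is "A medication with a completely missing start date will be considered a prior medication". The second is "A medication with a missing stop date will be considered a concomitant medication". Neither refers to the other date. Table 1 in the same section imputes partial dates only, where at least the year is known.

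The classes are defined in three places:

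- SAP 7.4.1: "Prior medications are medications that were stopped ≥ 28 days prior to screening visit".
- SAP 7.4.2: "Concomitant medications are any medications started between 28 days prior to Screening through the End of Study visit".
- Protocol 12.10.8: "Concomitant medications are medications taken at least once from 28 days prior to Screening through the End of Study visit". It adds that a drug stopped at the 28-day point does not count as concomitant.

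SAP 7.4 gives the two classes separate listings and separate summaries. SAP Section 11 enters NA for changes from the protocol's analysis.

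For adverse events, 6.3 does consult the other date. With a missing onset, "then the AE will be considered a TEAE unless a non-missing stop date indicates otherwise".

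**The concern.** A rule meant to separate two classes should put each record into one of them, and into the class that the definitions intend. Section 6.3 decides on the missing date alone. A stop date on study is direct evidence that the drug was used inside the window, yet the rule ignores it. When the stop date is also absent, two sentences apply and they disagree.

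What is at stake is the accuracy of the descriptive account of drugs used during the trial. This cohort requires stable background diabetes and NASH therapy and restricts lipid-lowering and weight-loss agents (Protocol 8.1 and 9.7), so a reader will look to the concomitant table for on-study use of such drugs. A record filed as prior is missing from that table. Where two sentences conflict, the count can depend on which one is programmed.

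**Working it through.** The plan states no figure on this point and no power or sample-size formula applies. The check is to take a completely missing start date, vary the stop date, and read off the class from each rule.

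| Stop date | SAP 6.3 | SAP 7.4.1 | Protocol 12.10.8 | Result |
|---|---|---|---|---|
| (a) Recorded, later than 28 days before Screening (for example on study) | prior | not prior | concomitant | misfiled |
| (b) Missing | prior and concomitant | cannot be shown | not settled by the dates | contradictory |
| (c) Recorded, at least 28 days before Screening | prior | prior | prior | correct |

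**Pattern (a).** The stop date shows use inside the window, so the protocol definition is met and the SAP's own definition of prior fails. SAP 7.4.2 cannot rescue the record, because it depends on a start date that is unknown.

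**Pattern (b).** Both sentences of 6.3 apply. Protocol 9.7 asks sites to record therapies from 28 days before Day 1 to end of study, which makes concomitant the more natural default, but the dates alone do not prove it. The SAP also does not say whether a drug marked as ongoing counts as having a missing stop date. If it does, the record falls under (b). If it does not, only the first sentence applies and an ongoing drug is filed as prior.

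**Pattern (c).** All the sources agree.

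**Can a drug be in both classes by design?** No. Section 6.3 says that the rules distinguish the classes, and 7.4.1 defines prior by a stop before the window, so a drug used on study cannot qualify.

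**Is the 7.4.2 wording the whole problem?** No. Take a known start 400 days before Screening and a known stop on study. Section 6.3 does not apply, 7.4.1 is not met, and 7.4.2 is not met because the drug started before the window. The protocol makes it concomitant. That is a separate gap in 7.4.2. Closing it would leave both sentences of 6.3 in force, so (a) and (b) would remain.

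**After the change set out under fix:** (a) becomes concomitant only, (b) becomes concomitant only, (c) stays prior, and the drug with the known old start becomes concomitant.

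**The case against.** The best case on the other side is that this is rare and harmless.

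- **Rarity.** Definite misfiling needs a wholly absent start date together with a recorded stop inside the window. If the year is known, Table 1 applies. Eligibility turns on 3 or 12 months of stable use for diabetes drugs, statins and NASH therapies, so sites will often have at least a partial date. This stands as a limit on frequency.
- **Information available elsewhere.** Statin and type 2 diabetes status are baseline summaries (SAP 7.2), study rosuvastatin has its own administration and compliance listings, and incomplete data are listed as reported. This stands: no record is lost, though a misfiled one sits in the wrong listing.
- **Redaction.** SAP Section 14 (Programming Considerations) and the table index are blacked out, and the mock-ups are separate documents. A precedence rule could sit there. For (b) the claim must therefore be restricted to the visible text. A tie-break between the two sentences would not help (a), where only the first sentence applies.
- **The adverse-event rule is a safety convention.** Agreed. Nothing obliges the medication rule to copy it. It shows only that the section can consult a second date.

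A reader might also infer that long-term statins, diabetes drugs and NASH therapies are moved wholesale to the prior table, so that their on-study use is understated. The documents do not support that. Such drugs are usually ongoing. If ongoing is read as a missing stop date, they fall under the conflicting second sentence, which calls them concomitant. Nothing in the documents says that start dates are mostly missing for them.

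**Conclusion.** The point holds as a defect in a stated rule. For a completely missing start date, 6.3 gives a wrong class in pattern (a) and, on the visible text, two classes in pattern (b). Its reach is the prior and concomitant medication tables and listings. The efficacy tests are not affected: the ANCOVA in SAP 8.2.1 uses treatment, fibrosis stage, the baseline value and baseline ALT, and no medication class.

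Two stronger readings should be set aside. One is a count of affected records. Assuming 5 drugs for each of 75 subjects and 2% to 10% missing starts gives 375 × 0.02 = 7.5 to 375 × 0.10 = 37.5 records. Only the 75 comes from the documents, and the product includes pattern (c), which is classified correctly. It is not an estimate of misfiled records. The other is that misfiling would let prohibited drugs escape the deviation review in SAP 5.6 and so alter the Per Protocol population. The documents do not say that this review works from the prior/concomitant label.

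The conclusion assumes that a recorded stop date is the last date of use. Priority is low: worth correcting because it is cheap.

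**What to change.** Replace the two medication sentences in SAP 6.3 with:

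*A medication with a completely missing start date is concomitant unless its stop date (after Table 1 imputation) is at least 28 days before Screening. A medication with a missing stop date is treated as ongoing and is concomitant.*

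In the same edit, reword SAP 7.4.2 so that it follows Protocol 12.10.8 and defines a concomitant medication by use at least once in the window, not by a start within it. Without this second change, an old drug with an unknown start and an on-study stop would be concomitant while the same drug with a known old start would meet neither SAP definition. With both changes each record gets exactly one class.

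The cost is two sentences in 6.3, one in 7.4.2 and a small code change, to be made before database lock. The edit keeps the Screening anchor of 12.10.8. It does not reconcile that anchor with Protocol 9.7, which starts recording 28 days before Day 1; that can be noted separately.

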6.4. VISIT WINDOWS

No visit windowing will be applied to assessments—the nominal visit name/time point will be used in statistical summaries.

6.5. POOLING OF CENTRES

Data from all investigational centers will be pooled for summaries and analyses.

6.6. SUBGROUPS

Not applicable for this study.

Amendment Final V 2.0

7. DEMOGRAPHIC, OTHER BASELINE CHARACTERISTICS AND MEDICATION

7.1. SUBJECT DISPOSITION AND WITHDRAWALS

The total number of subjects entered into the study and included in each analysis population will be summarized by actual treatment group and overall. The number of subjects prematurely discontinuing from treatment and study, along with the reason for early termination will be summarized.

Individual data listings for subject disposition will be presented for each subject, including enrollment date, treatment start date, treatment discontinuation date, study discontinuation date, discontinuation reason, and population flags.

Subject disposition will be summarized using the ITT population.

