#### **12.4.1 Intent-to-Treat Population**

All randomized subjects in the double-blind and placebo-controlled 24-week histology cohorts) will be included in the Intent-to-Treat (ITT) population. All Baseline characteristics and demographic data will be summarized using the ITT population. The ITT population will be based on randomized treatment if this differs from actual treatment received.

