#### **12.6 Patient Disposition**

Individual data listings for patient disposition will be presented for each patient, including enrollment date, treatment start date, treatment discontinuation date, discontinuation reason, and population flags. The number and percentage of patients entering and discontinuing the study will be presented by randomized treatment group for the double-blind and placebo-controlled 24-week histology cohorts and by enrolled treatment group for the open-label single-blind cohort. The reasons for discontinuation will also be summarized. Patient disposition will be summarized using the ITT population for the double-blind and placebo-controlled 24-week histology cohorts and the All Patients population for the open-label single-blind cohort.

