5. ANALYSIS POPULATIONS

5.1. INTENT-TO-TREAT POPULATION

All randomized subjects will be included in the Intent-to-Treat (ITT) population. The ITT population will be used to summarize subject enrollment and disposition and will be based on randomized treatment if this differs from actual treatment received.

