5.3. EFFICACY POPULATION

The Efficacy Population will include all enrolled subjects who receive at least one dose (full or partial) of NGM282 and have at least one valid, non-missing post-dose efficacy/PD parameter value.

All efficacy and PD endpoints will be summarized and analyzed using the Efficacy population. This will be the main population for the analysis of efficacy and PD endpoints. The Efficacy population will be based on enrolled treatment if this differs from actual treatment received.

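### SAP 7.1 counts subjects entered and each analysis population by actual treatment, against the randomised grouping in SAP 5.1 and protocol 12.6; SAP 7.3 also moves medical history off the ITT population

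*SAP*

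**What the plan says.** SAP 7.1 covers disposition in three sentences. The first gives the grouping: subjects entered and those "included in each analysis population will be summarized by actual treatment group and overall". The second covers withdrawals and names no grouping: "The number of subjects prematurely discontinuing from treatment and study, along with the reason for early termination will be summarized". The third names the population: "Subject disposition will be summarized using the ITT population".

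SAP 5.1 defines that population: "All randomized subjects will be included in the Intent-to-Treat (ITT) population". There is no dosing requirement. It assigns ITT to the enrolment and disposition summaries and says that it "will be based on randomized treatment if this differs from actual treatment received".

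Protocol 12.6 says that the numbers entering and discontinuing in this cohort "will be presented by randomized treatment group", and the Statistical Methods part of the synopsis agrees.

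On the other populations, SAP 5.2 groups the Safety population by actual treatment, while SAP 5.3 says: "The Efficacy population will be based on enrolled treatment if this differs from actual treatment received".

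On baseline data, protocol 12.4.1 says: "All Baseline characteristics and demographic data will be summarized using the ITT population". Protocol 12.8 repeats this and includes medical history. SAP 7.3 summarises medical history on the Efficacy and Safety populations. SAP 7.2 names no population for demographics. SAP 11, the section for changes from the protocol, reads NA.

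**The concern.** ITT membership depends only on randomisation. Actual treatment depends on what was injected. Grouping an ITT count by actual treatment therefore leaves a randomised, never-dosed subject with no column, and puts a subject who received the wrong kits in the arm to which he or she was not randomised. The visible SAP text gives no rule for either case.

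The same sentence covers every analysis population. Actual treatment suits the Safety count. It does not suit the Efficacy count, so the Efficacy Ns in the disposition table could differ from those in the efficacy tables, which follow SAP 5.3.

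The medical-history rule is a separate departure from the protocol. The Efficacy and Safety populations both require a dose and a post-dose value, so the randomised groups would be described on subsets fixed after randomisation.

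At stake is whether the disposition and medical-history tables describe the groups as randomised and agree with the rest of the report.

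**Working it through.** **Planned size, which supplies the denominators.** SAP 3.5 gives 50% against 15% response, 80% power, two-sided alpha 0.05, 2:1 allocation and 15% dropout. With the usual two-proportion formula without continuity correction, p1 = 0.15, p2 = 0.50, r = 2 and pooled p = (0.15 + 2 × 0.50)/3 = 0.383:

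n(placebo) = [1.96 × √(0.383 × 0.617 × 1.5) + 0.842 × √(0.15 × 0.85 + 0.50 × 0.50/2)]² / 0.35² = 20.6, rounded up to 21.

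That is 21 + 42 = 63 evaluable, and 63/0.85 = 74.1, rounded up to 75 (25 + 50). The plan's figure reproduces and is not in dispute.

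**The rules side by side.**

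| Count | SAP 7.1 | Population's own rule |
|---|---|---|
| Entered / ITT | actual | randomised (SAP 5.1; protocol 12.4.1, 12.6, synopsis) |
| Efficacy | actual | enrolled (SAP 5.3) |
| Safety | actual | actual (SAP 5.2) |
| Discontinuations | not stated | randomised (protocol 12.6) |

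SAP 7.1 conflicts with the first two rows, agrees with the third and is silent on the fourth. The SAP's Per Protocol and Liver Histology definitions are redacted and are not judged here.

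**Effect on the column totals.** By randomised treatment, the ITT columns are always 50 + 25 = 75. By actual treatment they depend on events. The documents give no counts, so these are assumed scenarios:

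| Scenario | NGM282 | Placebo | Sum of columns |
|---|---|---|---|
| None affected | 50 | 25 | 75 |
| 1 NGM282 subject never dosed | 49 | 25 | 74 |
| 3 never dosed (2 NGM282, 1 placebo) | 48 | 24 | 72 |
| 1 NGM282 subject given placebo | 49 | 26 | 75 |
| 1 placebo subject given NGM282 | 51 | 24 | 75 |

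**Effect on a placebo dropout rate**, if discontinuations were also grouped by actual treatment. At the planned 15%, 0.15 × 25 = 3.75, taken as 4, so 4/25 = 16.0%. One affected subject gives:

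- placebo dropout removed, because never dosed or moved to the other arm: 3/24 = 12.5% (−3.5 points)
- placebo completer moved out: 4/24 = 16.7% (+0.7)
- NGM282 completer moved in: 4/26 = 15.4% (−0.6)
- NGM282 dropout moved in: 5/26 = 19.2% (+3.2)

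**The case against.** The strongest defence is that the word actual governs only the entered and population counts. The discontinuation sentence names no grouping, SAP 6.1's default says only that tables are by treatment group, and SAP 7.1 ends by assigning disposition to a population that SAP 5.1 groups as randomised. Discontinuations by randomised arm is thus a fair reading. This stands. A reader might infer that the SAP hides differential dropout by arm, and so evidence on missing Week 24 scans and biopsies; the text does not go that far.

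A reader might also infer that never-dosed subjects vanish from the report. They do not: the counts are also given overall, and SAP 18 lists enrolment and disposition on ITT. What they lack is an arm column.

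Nor does each affected subject shift the placebo rate by 1/25 = 4 points. That holds the denominator at 25, whereas regrouping changes it, and moving a completer leaves the numerator alone.

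It is tempting to say that all baseline comparisons are put on post-randomisation subsets. Only medical history visibly is. SAP 7.2 is silent on population, the demographic listings are on ITT, the index of tables is redacted and the mock-ups are a separate document. SAP 5.1 does not confine ITT to enrolment and disposition either, since SAP 5.6 uses it for deviations.

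Finally, protocol 9.6.2 puts randomisation, kit dispensing and the supervised first injection in one Day 1 visit, so never-dosed subjects should be few. That limits the size of the problem. It does not remove the contradiction.

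**Conclusion.** The contradiction holds for the entered, ITT and Efficacy counts, and it is not declared in SAP 11. The medical-history population is a second undeclared departure from the protocol. Both are rules wrong as written, not missing detail.

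Severity is minor. The effect is confined to reporting tables; efficacy grouping is already fixed by SAP 5.3, and no efficacy estimate, test, alpha or power changes. With no never-dosed and no misallocated subject, the two groupings give identical tables. With one affected subject, the illustrative placebo dropout rate moves by about 0.6 to 3.5 points, and by under 1 point if that subject is a completer who is moved between arms. This range rests on three assumptions: the planned arm sizes, 4 placebo dropouts, and discontinuations following the actual grouping. How many subjects would be affected cannot be known from the documents.

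**What to change.** In SAP 7.1, give entered, ITT and discontinuation counts by randomised treatment group, with a row in each arm for subjects randomised but not dosed. Count every other population by its own rule: Efficacy by enrolled treatment (here, randomised), Safety by actual treatment, and the remaining populations as their definitions state.

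In SAP 7.2 and 7.3, name the ITT population for the demographic, baseline and medical-history tables, as protocol 12.4.1 and 12.8 require. If medical history is also wanted on the Efficacy or Safety population, keep that as an addition and record it in SAP 11.

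The cost is a change of wording in 7.1 and a sentence each in 7.2 and 7.3, with matching table shells. No extra data are needed.

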7.2. DEMOGRAPHIC AND OTHER BASELINE CHARACTERISTICS

Demography (age, sex, race, ethnicity, type 2 diabetic status, cirrhosis status, cardiovascular event status, statin status, height, body weight, BMI and waist circumference at screening), will be summarized, by Steatosis score [Overall, 0 (< 5%), 1 (5%-33%), 2 (34%-66%) and 3 (> 66%)] and treatment group.

Individual data listings for demographic and baseline characteristics will be presented for each subject.

Age = (date signed informed consent - date of birth + 1) / 365.25 and truncated to complete years.

Height (cm) = height (inches) * 2.54

Weight (kg) = weight (lbs) * 0.4536

BMI (kg/m²) = Weight(kg)/[Height(m)²]

Previous Diagnoses including cirrhosis, diabetes, cardiovascular events/diseases, ..., etc. will also be summarized descriptively by presenting the number and percent of subjects reporting a history of each condition.

